9.3.6 Safety Analyses

Safety assessments will include TEAEs, physical examination, vital signs, body weight, Columbia Suicide Severity Rating Scale (C-SSRS), laboratory results, Electrocardiograms (ECG), vital signs and body weight, and direct questioning to assess for sleep, appetite, mood and psychotic events.

All safety data will be analyzed descriptively by treatment group.

The frequency of subjects reporting AEs will be summarized within each system organ class and preferred term.

9.3.6.1 Adverse Events

All AEs will be coded using Medical Dictionary for Regulatory Activities (MedDRA) Version 20.0. Treatment-emergent AEs, any AEs recorded during the study at least one dose of study medication, will be summarized and categorized by severity and relationship to the investigational drug. If a subject has more than one occurrence of the same AE, he/she will be counted only once within that preferred term in the summary tables. The most severe occurrence of an AE, as well as the most extreme relationship of the AE to the study procedures or investigational drug, will be indicated in cases of multiple occurrences of the same AE. Serious adverse events and AEs of special interest, which will be defined in the SAP, will also be summarized separately. All AEs will be presented in a listing. Additionally, listings of SAEs and AEs leading to discontinuation will be generated. All SAEs will be evaluated to determine whether they are Unexpected Adverse Reactions.

9.3.6.2 Columbia Suicide Severity Rating Scale (C-SSRS)

The frequency of suicidality using the C-SSRS will be summarized by treatment group for the number of subjects reporting at least 1 occurrence of suicidal ideation or behavior, the number of subjects reporting any type of suicidal behavior, and the number of subjects reporting any type of suicidal ideation.

9.3.6.3 Questionnaire for Sleep, Appetite, Mood, and Psychotic Adverse Events

Occurrences related to sleep, appetite, mood, and psychotic events will be summarized descriptively by treatment and time point.

9.3.6.4 Clinical Laboratory Evaluations

Laboratory test results will be summarized descriptively by treatment and time point as both observed values and change from baseline values.

The number of subjects with clinical laboratory values below, within, or above the normal range by time point and in relation to baseline will be tabulated for each clinical laboratory analyte by treatment group (shift table).

Laboratory values that are outside the normal range will be flagged in the data listings.

9.3.6.5 Vital Signs and Body Weight

Descriptive summaries of actual values and changes from Baseline will be calculated for vital signs and weight.

Confidential Page 52 of 67

9.3.6.6 Electrocardiograms (ECG)

The number and percentage of subjects with normal and abnormal ECG results will be summarized for the Safety Population by study phase and treatment group.

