3.4 Exclusion Criteria

The presence of any of the following exclusion criteria precludes a subject from study enrollment:

- 1. Current or lifetime history of bipolar disorder or any psychotic disorder as established by Mini International Neuropsychiatric Interview (M.I.N.I.) 7.0.2.
- 2. Current history of major depression generalized anxiety disorder, obsessive-compulsive disorder, panic disorder, or post-traumatic stress disorder as established by the M.I.N.I. 7.0.2.
- 3. Known history of chronic medical illnesses including untreated thyroid disease, peripheral vasculopathy, known structural cardiac disorders, serious cardiac conditions, serious arrhythmias, cardiomyopathy, and known family history of sudden death.
- 4. History of uncontrolled hypertension or a resting systolic blood pressure >140 mmHg or diastolic blood pressure >90 mmHg. Subjects with well-controlled hypertension on a stable dose for at least 3 months of anti-hypertensives will be allowed to participate.
- 5. Have clinically significant findings in vital signs measurements at Screening including:
 - Systolic blood pressure >140 mmHg or diastolic blood pressure >90 mmHg
 - Heart rate >100 bpm
- 6. Known history or presence of significant renal or hepatic disease, as indicated by clinical laboratory assessment (clinically significant liver function tests, blood urea nitrogen, or creatinine levels)
- 7. Clinically significant abnormal electrocardiogram or cardiac findings on physical examination (including the presence of a pathologic murmur).
- 8. Use of the following medications within 14 days of Baseline Visit:
 - Atomoxetine
 - Monoamine oxidase inhibitors (e.g., selegiline, isocarboxazid, phenelzine, tranylcypromine)
 - Tricyclic antidepressants (e.g., desipramine, protriptyline).
- 9. Use of the following medications within 3 days of Baseline Visit:

Confidential Page 24 of 67

- Gastrointestinal acidifying agents (e.g., guanethidine, reserpine, glutamic acid hydrochloride [HCl], ascorbic acid)
- Urinary acidifying agents (e.g., ammonium chloride, sodium acid phosphate, methenamine salts).
- 10. Use of fluoxetine within 30 days of Baseline Visit.
- 11. Use of stimulant medications within 1 week of Baseline Visit.
- 12. Planned use of prohibited drugs or agents from the Screening visit through the end of the study.
- 13. Participation in a clinical study in which an investigational drug was administered within 30 days prior to Screening.

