3.6 Subject Withdrawal Criteria

Within the provisions of informed consent and good clinical judgment with respect to the subject's safety, every attempt should be made to have subjects complete the study. The following are possible reasons to terminate the participation of any subject from the study:

Confidential Page 25 of 67

- Signs and symptoms of intolerance to the study medication.
- A treatment-related, serious adverse event (SAE) is observed.
- The subject is grossly non-compliant, as determined by the Investigator.
- Continued participation, in the opinion of the Investigator, is no longer in the best interest of the subject.
- The subject wishes to withdraw for any reason.
- Unblinding of the Investigator, site personnel performing assessments, or subject to a subject's treatment assignment.

Subjects will be encouraged to adhere to the protocol and complete all required assessments for the study. A subject may also be discontinued from the study for any of the following medical and/or administrative reasons:

- Pregnancy
- At the discretion of the Investigator at any time
- At the subject's request
- Occurrence of a Treatment Emergent Adverse Event (TEAE) or considerable worsening of an AE that represents an unacceptable risk to the subject and when continued participation in the investigational study is not warranted, in the judgment of the Investigator or the Sponsor. The Investigator must follow the subject until the AE resolves or satisfactorily stabilizes.

Any enrolled subjects desiring to discontinue prior to study completion should be encouraged to continue in the study and adhere to the protocol and subsequent regularly scheduled safety and effectiveness evaluations. Subjects who are discontinued outside of any scheduled visit will be encouraged to complete the final study visit at the time of withdrawal. Subjects who are discontinued during a scheduled visit will be encouraged to complete all assessments for both that study visit and the final study visit at the time of withdrawal. A subject who withdraws following study drug administration will not be replaced in their cohort.

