9 STATISTICAL CONSIDERATIONS

This is a phase 3 randomized, double-blind (DB), placebo-controlled, parallel, study to assess the efficacy and safety of AMPH ER TAB compared to placebo for the treatment of ADHD in adults aged 18 to 60 years. The objective of the statistical analysis will be to evaluate the efficacy and safety of AMPH ER TAB compared to placebo in adult patients with ADHD aged 18 to 60 years.

All continuous study assessments will be summarized by treatment and time point using descriptive statistics (n, mean, median, standard deviation, minimum, and maximum). All categorical study assessments will be summarized by treatment and time point using frequency counts and percentages. Hypothesis testing, unless otherwise indicated, will be two-sided and performed at the 0.05 significance level.

A detailed statistical analysis plan (SAP) will be written and finalized prior to unblinding of the data.

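### The ECG summary gives unpaired normal/abnormal counts, so it cannot show how many subjects became newly abnormal on treatment; a shift table would

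*Combined protocol and SAP*

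**What the plan says.** **ECG.** Section 9.3.6.6 reads: "The number and percentage of subjects with normal and abnormal ECG results will be summarized for the Safety Population by study phase and treatment group". Appendix A schedules ECGs at Screening and at (or within 2 days of) Visit 5, with a further ECG at unscheduled visits on request, and requires central reading.

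**Entry.** Exclusion 7 in section 3.4 bars a subject for "Clinically significant abnormal electrocardiogram or cardiac findings on physical examination (including the presence of a pathologic murmur"). An ECG that is abnormal but not clinically significant does not exclude.

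**Laboratory values.** Section 9.3.6.4 plans a paired display: "The number of subjects with clinical laboratory values below, within, or above the normal range by time point and in relation to baseline" is tabulated per analyte and arm, and the protocol calls this a shift table.

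**Vital signs.** Section 9.3.6.5 reads: "Descriptive summaries of actual values and changes from Baseline will be calculated for vital signs and weight". Section 9 says what descriptive means: "All continuous study assessments will be summarized by treatment and time point using descriptive statistics (n, mean, median, standard deviation, minimum, and maximum"). The limits in section 3.4, "systolic blood pressure >140 mmHg or diastolic blood pressure >90 mmHg" and "Heart rate >100 bpm", serve as entry criteria and are not used in any on-treatment summary.

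**Withdrawals.** The early-termination list in section 4.2.10.6 does not name an ECG, but it allows other assessments that the investigator chooses. Section 3.6 adds: "Subjects who are discontinued outside of any scheduled visit will be encouraged to complete the final study visit at the time of withdrawal".

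**SAP.** Section 9 promises a detailed SAP before unblinding. Its text is not in the file.

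**The concern.** The safety objective is to assess the safety and tolerability of an amphetamine, and a natural question is how many subjects with a normal ECG before treatment had an abnormal one on it. Counts by phase and arm do not answer that. An abnormal result at Visit 5 may be new or may have been there at Screening, and a new one can be offset by another that resolved. Section 9.3.6.4 shows that the authors specified a paired table where they wanted one, so section 9.3.6.6 is hard to read as implying one.

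Without pairing, the per-arm number of new ECG abnormalities would have to come from adverse events. Those depend on what investigators judge clinically relevant (section 8.3.1).

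**Working it through.** The plan gives no figure to reproduce on this point. The check is how far the planned table pins down the number of new cases.

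**Inputs.** Section 9.1 plans about 108 subjects, 92 completers and 15% dropout. The allocation ratio is not stated; 1:1 is assumed, giving 108/2 = 54 enrolled and 92/2 = 46 completers per arm. The documents give no ECG abnormality rate, so all abnormal counts below are assumptions.

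**Formula.** Take n subjects with both ECGs, a0 abnormal at Screening and a1 abnormal on treatment. The table fixes only the net change: new − resolved = a1 − a0. The number of new cases lies between max(0, a1 − a0) and min(a1, n − a0), out of the n − a0 who were normal at Screening.

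**Results, n = 46.**

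| Abnormal at Screening | Abnormal at Visit 5 | New cases | Normal at Screening | Share newly abnormal |
|---|---|---|---|---|
| 4 | 4 | 0 to 4 | 42 | 0% to 10% |
| 8 | 8 | 0 to 8 | 38 | 0% to 21% |
| 12 | 12 | 0 to 12 | 34 | 0% to 35% |
| 8 | 12 | 4 to 12 | 38 | 11% to 32% |

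With n = 54, 8 and 8 again fit 0 to 8, now out of 46 (8/46 = 17%). If nobody is abnormal at Screening, the number of new cases equals a1 and the planned table suffices. Exclusion 7 does not guarantee that.

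**Subjects with no on-treatment ECG.** At 15% dropout, 0.15 × 54 = 8.1, so at most about 8 per arm (5.4 at 10% dropout, 10.8 at 20%). If half of those withdrawing have an ECG, about 4 per arm lack one; if all do, none.

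**Blood pressure.** Assume on-treatment systolic pressure is normally distributed. The expected number above 140 mmHg among 54 is 54 × [1 − Φ((140 − mean)/SD)]:
- mean 122, SD 10: z = 1.80, 3.6%, about 2 subjects
- mean 122, SD 12: z = 1.50, 6.7%, about 4 subjects
- mean 125, SD 12: z = 1.25, 10.6%, about 6 subjects

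The planned mean, SD and maximum therefore place the count roughly, without stating it or saying who is newly above the limit.

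**The case against.** The strongest reply is randomisation. The ECG table is by arm, pre-existing abnormalities are balanced between arms in expectation, and the Screening counts would show a chance imbalance. A drug that raises the rate of abnormal ECGs would appear in the Visit 5 contrast with placebo without pairing. This stands. A reader might infer that the table could hide a drug effect: if both arms print 8 and 8, the difference in new cases could in logic reach 8/38, or 21 percentage points, either way. That extreme needs all 8 Screening abnormalities in one arm to resolve and 8 others to appear, with no change at all in the other arm. Nothing in the documents makes that plausible.

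A reader might also infer that blood pressure and pulse have no within-subject summary. Section 9.3.6.5 plans changes from Baseline, so they do. Arithmetic bounds on the count above 140 can be made wide (1 to 9 of 46 for one assumed set of printed statistics), but the upper end needs a contrived distribution. The ECG gap is the firmer one.

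Nor do the documents support reading the early-termination list as leaving all withdrawals without an ECG. Sections 3.2.3, 3.6 and 4.2.10.6 each give a route to one, so this gap is at most partial. A shift table would display it but not repair it.

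Two further replies hold in part. Clinically relevant new findings should be reported as adverse events (sections 8.1 and 8.3.1) and summarised (section 9.3.6.1), so what goes uncounted is mainly findings that nobody judged relevant. And shift tables are the kind of detail a SAP supplies. The absence of SAP text in the file does not show that they were never planned, but neither does a promised SAP change the method that section 9.3.6.6 states.

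**Conclusion.** The point holds for ECGs, at low priority. As written, section 9.3.6.6 yields the net change in abnormal ECGs by arm but not the number of subjects newly abnormal. The uncertainty grows with the number abnormal at Screening: 8 and 8 in 46 subjects fit 0 to 8 new cases. These sizes rest on assumed counts and 1:1 allocation. The logic needs only that some subjects enter with an abnormal ECG, which exclusion 7 permits.

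For blood pressure and pulse, a count of subjects newly above a limit would be useful beside the planned changes from Baseline, but it is optional and noisier.

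All safety analysis is descriptive, so the efficacy result, the error rate and every decision rule are untouched. If the separate SAP already contains these tables, nothing needs to change.

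**What to change.** In section 9.3.6.6, or in the SAP before unblinding, replace the unpaired counts with a shift table of Screening against on-treatment ECG (normal/abnormal), by arm, in the Safety Population. Include unscheduled and discretionary ECGs, and add a category for subjects with no on-treatment ECG. This follows the format already planned for laboratory values.

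Optionally, in section 9.3.6.5, keep the planned summaries and add by arm the number and percentage of subjects with any reading after the first dose above 140 mmHg systolic, 90 mmHg diastolic or 100 bpm who were not above that limit at Baseline.

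The cost is SAP wording and one or two tables. ECGs are already centrally read, and blood pressure and pulse are taken at every visit, before and about 3 hours after dosing at Visits 4 and 5. The drawback of the optional count is measurement noise. In a simulation with no drug effect (between-subject SD 10, Screening and Baseline both at or below 140, seven later readings), 11.5% of subjects crossed 140 systolic at least once with a true mean of 120 and a reading SD of 7. The range was 2.6% to 28.8% over true means of 115 to 125 and reading SDs of 5 to 9; all of these inputs are assumptions. The count therefore has to be read against placebo, not on its own.

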9.3.7 Other Statistical Considerations

9.3.7.1 Significance Levels

The type I error significance level for each set of study analyses as applicable will be set at alpha = 0.05.

To preserve the family-wise error rate of 0.05, a gatekeeping testing procedure will be implemented for primary/secondary efficacy endpoints in the following order:

- PERMP-T scores over all post-dose time points assessed at Visit 5
- PERMP-T scores at 4, 2, 8, 10, 12, 1, 0.5, 13 and 14 hours post-dose

The above will test in sequence whether a significant treatment effect is present using the models previously specified. If a significant effect is noticed, the following test will then be examined until all endpoints are exhausted or failure to reject the null hypothesis is met at alpha = 0.05.

9.3.7.2 Missing Data

No imputation of missing PERMP scores will be done for the primary efficacy analysis. To evaluate the sensitivity of the primary analysis results to the use or non-use of imputation, analyses using multiple imputation methods will be conducted as mentioned in Section 9.3.5.1. Additional details will be described in the SAP.

9.3.8 Visit Windows

All data collected will be displayed and analyzed according to the actual visit data in the eCRF. Study visits may occur within a \pm 3-day window of the weekly scheduled visit and ensuring that the maximum length of exposure to the Investigational Product prior to Visit 5 shall be 35 (\pm 3) days. The maximum dose of AMPH ER TAB 20 mg (or matching placebo) will be administered for 14 (\pm 3) days prior to visit 5.

Assessments taken outside of windows described in the protocol will be displayed according to the eCRF assessment recorded by the Investigator.

Confidential Page 53 of 67

10 DIRECT ACCESS TO PROCEDURAL DOCUMENTS

10.1 Study Monitoring

According to Good Clinical Practices (GCP) guidelines, the Sponsor of the study is responsible for ensuring the proper conduct of the study with regard to protocol adherence and validity of data recorded on the eCRFs. The contract research organization (CRO) is responsible for assigning the study monitor(s) to this study, with prior approval from the Sponsor. The study monitors' duties are to aid the Investigator and the Sponsor in the maintenance of complete, accurate, legible, well-organized, and easily retrievable data. The study monitor will advise the Investigator of the regulatory necessity for trial-related monitoring, audits, IRB review, and inspection by providing direct access to the source data/documents. In addition, the study monitor will explain to and interpret for the Investigator all regulations applicable to the clinical evaluation of an investigational drug as documented in ICH guidelines.

It is the study monitors' responsibility to inspect the eCRFs throughout the study to protect the rights of the subjects; to verify adherence to the protocol; to verify completeness, accuracy, and consistency of the data; and to confirm adherence of study conduct to any local regulations. Details may be outlined in the study monitoring plan.

10.2 Source Documents

Tris Pharma requires that the Investigator prepare and maintain adequate and accurate records for each subject treated with the investigational drug. Source documents such as any hospital, clinic, or office charts and the signed ICFs are to be included in the Investigator's files with the subject's study records.

Data will be captured electronically. Study site personnel will record eCRF data from source documents. If any data are first recorded onto documents such as laboratory reports, these documents will be considered source.

10.3 Data Collection and Management

This study will use electronic data collection techniques to collect data directly from the investigational site using eCRFs. The data will be stored centrally in a fully validated clinical database compliant with FDA regulations on electronic data integrity. The Investigator is responsible for ensuring that all sections of each eCRF are completed promptly and correctly and that entries can be verified against any source data.

Study monitors will perform 100% source document verification to ensure there are no inconsistencies between the eCRFs and source documents. Discrepancies will be resolved in accordance with the principles of GCP. Detailed study monitoring procedures are provided in the Clinical Monitoring Plan.

At intervals throughout the study and upon completion, data will be exported from the database into SAS datasets.

Data management will be coordinated by the data managers of the designated CRO in accordance with their SOPs for data management and a formal study data management plan. The data managers will provide a quality control statement following database lock.

Adverse events will be coded with MedDRA. Concomitant medications will be coded using World Health Organization – Drug Reference List.

Confidential Page 54 of 67

11 QUALITY CONTROL AND QUALITY ASSURANCE

Quality assurance includes all the planned and systematic actions that are established to ensure that the clinical study is performed, and the data are generated, documented (recorded), and reported according to ICH GCP and local/regional regulatory standards.

A quality assurance representative from Tris Pharma (or a qualified delegate), who is independent of and separated from routine monitoring, may periodically arrange inspections/audits of the clinical study by reviewing the data obtained and procedural aspects. These inspections may include on-site inspections/audits and source data checks. Direct access to source documents is required for the purpose of these periodic inspections/audits.

Confidential Page 55 of 67

12 ETHICS

12.1 Ethics Review

This research will be carried out in accordance with GCP as set out by the ICH Guidance for Industry, E6(R2) GCP: Good Clinical Practice; the basic principles defined in the U.S. Code of Federal Regulations (21 CFR Part 312); the World Medical Association Declaration of Helsinki (Fortaleza, Brazil, October 2013); and in accordance with all national, state, and local laws and regulations.

12.2 Ethics Committees

The Investigator (or Sponsor, where applicable) is responsible for ensuring that this protocol, the site's ICFs, and any other information that will be presented to potential subjects (e.g., advertisements or information that supports or supplements the ICF) are reviewed and approved by the appropriate IRB. The Investigator agrees to allow the IRB direct access to all relevant documents. The IRB must be constituted in accordance with all applicable regulatory requirements. The Sponsor will provide the Investigator with relevant documents or data needed for IRB review and approval of the study. Before investigational products can be shipped to the site, the Sponsor must receive copies of the IRB approval, the approved ICF, and any other information that the IRB has approved for presentation to potential subjects.

If the protocol, the ICFs, or any other information that the IRB has approved for presentation to potential subjects is amended during the study, the Investigator is responsible for ensuring that the IRB reviews and approves, where applicable, these amended documents. The Investigator must follow all applicable regulatory requirements pertaining to the use of an amended ICF, including obtaining IRB approval of the amended form, before new subjects consent to take part in the study using the new version of the form. The Investigator must promptly forward to the Sponsor copies of the IRB approval of the amended ICF or other information and the approved amended ICF or other information. IRB approval of the consent forms must be obtained in addition to the approval given for the clinical study.

